12 MECHANISTIC ASSAYS

As discussed in other sections of the protocol, we propose that the substitution of belatacept for tacrolimus will result in better preservation of renal function. However, the results of the phase II and phase III studies conducted to date suggest that belatacept, at least as used in those studies, may be associated with a slightly increased risk of acute alloimmune-mediated graft injury and an increased risk of PTLD, which is most commonly a consequence of an active EBV infection. Consequently, our areas of focus include determinations of renal function, viral infections, and alloimmunity. Mechanistic assays will be paired with clinical measurements in an attempt to gain insights into the mechanisms responsible for the hypothesized differences between the 2 treatment groups.

Study participants will be informed that they may be approached about additional clinical evaluations or studies that have received the full approval of the NIAID as new evaluations are identified. If additional evaluations or studies are determined to be desirable, this protocol (and other appropriate study documents, (e.g., the informed consent and the statistical analysis plan) will be amended and submitted to the appropriate regulatory authorities, ethics committees, and IRBs for approval. Each participant's signature will be obtained on the revised informed consent form before additional evaluations are performed. The specimens from these evaluations may be stored up to the end of the grant – approximately 5 years, or longer if the grant is extended.

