13.2.3 Mechanistic Assay Analyses

The primary mechanistic objective of CTOT studies is to identify and elucidate pathophysiologic and genetic mechanisms that are associated with allograft rejection and how these associations may evolve over time and/or differ between therapeutic treatments. In this study, the principal objectives of the mechanistic analyses of data from subjects receiving kidney or pancreas transplants will include assessment of the association between treatment (i.e., belatacept vs. tacrolimus maintenance) and renal function, incidence of viral infection and autoimmunity.

Ten mechanistic assays are described in Section 12. There are from 1 to 3 separate correlations or tests desired for each assay category and these are described in Table 8. The analysis numbers in the table refer to the following 10 assays:

- 1. Intracellular cytokine staining and viral phenotyping
- 2. Flow cytometry
- 3. Protein Assays
- 4. Gene expression, mRNA profiling
- 5. Anti-HLA alloantibodies and non-HLA antibodies
- 6. Autoimmunity markers
- 7. Genomics (gene polymorphisms)
- 8. Renal histology
- 9. Renal immunohistochemistry
- 10. Pancreatic histology
- 11. Viral testing (viral load determination)

Depending on the scale of measurement of the endpoints, the amount of missing data, and the questions of interest, exploratory data analysis (EDA) and/or statistical hypothesis testing and modeling will used. Given the small sample sizes (n=30 in each of 2 treatment arms), modeling and testing will generally be restricted to the continuous endpoints where the focus will be testing for treatment and time effects on repeated measures of the endpoints. These types of analyses will have sufficient sample sizes to make reasonable inferences; e.g., repeated measures ANCOVA tests for differences in gene expression in the treatment arms, over 5 assessment times would have to following degrees of freedom for the their error terms: treatment df = 58; time df = 238, time × treatment = 238.

Page 87 of 104

Analysis No.	Effector cells, antibodies, or markers (see Sect. 12)	Meas. Scale	Assay	Objective	Analysis Method ¹
1a	Virus-specific T- cell subpopulations	Continuous. (cell counts)	Cytokine staining + PCR	Correlation with viral loads detected with PCR, by visits and treatment arm	Spearman Rank Correlation Coeff., by visit and treatment group; treatment x time plots; tables of summary stats.

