1b	Virus-specific T- cell subpopulations	Binary	Cytokine staining + PCR	Comparison of prevalence of each T-cell type by visits and treatment arm	Contingency tables and Cochran Mantel Haenszel (CMH) tests
1c	Virus-specific T- cell subpopulations	Continuous. (cell counts)	Cytokine staining + PCR	Correlation with B-cell counts, NK cell counts, dendritic cell counts by visit and treatment arm	Spearman Rank Correlation Coeff., by visit and treatment group; treatment x time plots; tables of summary stats.
2a	Donor-reactive T- cell subpopulations	Continuous. (cell counts)	Flow Cytometry	Look for treatment arm differences in counts, over time	Random Effects repeated measures ANCOVA (RMANCOVA); treatment x time plots and random coefficients models and plots; tables of means and standard errors
2b	Donor-reactive T- cell subpopulations	Continuous. (cell counts)	Flow Cytometry	Correlation with eGFR, de novo anti-donor HLA and biopsy findings, by visits and treatment arm	Spearman Rank Correlation Coeff., by visit and treatment group; treatment x time plots; tables of summary stats.
3	Protein Assays				
4a	Gene expression data for > 128 markers	Continuous	Real -time PCR	Identify associations between specific mRNAs and the occurrence of AKI, CHI, CIT, and fibrosis, by visit pooled over trt	EDA: various graphical comparisons and descriptive statistics (by visit if there are enough occurrences of AKI, CKI, CIT, and/or fibrosis

¹ Statistical tests (e.g., t-tests) and statistical models (e.g., ANOVA) will only be performed if sample sizes are adequate

Page 88 of 104

Analysis No.	Effector cells, antibodies, or markers (see Sect. 12)	Meas. Scale	Assay	Objective	Analysis Method ¹
4b	Gene expression data for > 128 markers	Continuous	Real -time PCR	Look for evidence of treatment differences in the occurrence of each marker over time	Separate RMANCOVAs for each marker; treatment x time plots; tables of means and standard errors by marker, treatment arm, and visit
5a	Anti-HLA and non-Anti-HLA antibodies	Continuous	Luminex	Characterize the occurrence of HLA-A, B, C, DR, DQ α , DQ β , DP β , and anti- MICA, by treatment arm and visit	Separate RMANCOVAs for each ab.; treatment x time plots; tables of means and standard errors by antibody, treatment arm, and visit

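### Table 10, row 4a pools the arms with no account of treatment, so a drug-responsive gene can appear linked to injury when injury frequency also differs by arm

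*Combined protocol and SAP*

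**What the plan says.** Section 13.2.3, Table 10, row 4a covers "Gene expression data for > 128 markers". Its objective is "Identify associations between specific mRNAs and the occurrence of AKI, CHI, CIT, and fibrosis, by visit pooled over trt", and its method is "EDA: various graphical comparisons and descriptive statistics (by visit if there are enough occurrences of AKI, CKI, CIT, and/or fibrosis". Arm appears only in the instruction to pool over it. A footnote to the table adds: "Statistical tests (e.g., t-tests) and statistical models (e.g., ANOVA) will only be performed if sample sizes are adequate".

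Row 4b takes the same markers with a different aim: "Look for evidence of treatment differences in the occurrence of each marker over time". It uses one repeated-measures ANCOVA per marker and tabulates means by marker, arm and visit. Nothing in the plan carries the 4b results back into 4a.

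The correlation rows 1a, 1c, 2b and 5c are done by visit and treatment group. Row 6, the SNP row numbered 7, and row 9 do not mention arm. Row 4a is the only row that states that it pools over treatment.

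On what the arms are expected to do, section 12 states: "we propose that the substitution of belatacept for tacrolimus will result in better preservation of renal function". The same paragraph notes that belatacept may carry a slightly higher risk of acute alloimmune graft injury.

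**The concern.** A pooled comparison of injured and uninjured subjects is confounded by arm if arm affects both the marker and the frequency of injury. The documents make both effects plausible.

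- **Injury frequency.** The trial expects the arms to differ in renal outcome (section 12). The gene panel includes targets for calcineurin inhibitor toxicity (section 12.2.1), and the two arms have different tacrolimus trough targets (section 8, study therapy table).
- **Expression.** Belatacept acts by binding CD80 and CD86 and so blocking CD28 costimulation (section 2.1). CD28, CD80, CD86 and CTLA4 are all in Table 7. Row 4b exists because arm differences in expression are thought possible for any marker.

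What is at stake is how row 4a can be read. A difference in means between subjects with and without injury could reflect injury, or it could reflect which arm supplied more of the injured subjects. The pooled summary cannot separate the two. A drug effect in the opposite direction could also cancel a real association.

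**Working it through.** **The plan's own figures.** Row 4a has no sample size, alpha or power. The only figures given for gene expression are the error degrees of freedom for the repeated-measures ANCOVA in section 13.2.3, which is the row 4b type of analysis. With 60 subjects and 5 times, the treatment error df is 60 − 2 = 58, and the within-subject error df with linear time is 60 × 4 − 2 = 238. Both reproduce. They have no bearing on row 4a.

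**Inputs.** From the documents: 30 subjects per arm, allocated 1:1. Assumed, because the documents give neither: the injury rate in each arm (control p_C, investigational p_I), and the drug effect δ, which is the mean expression in control minus investigational, in within-arm SDs. The gene is taken to be unrelated to injury within each arm.

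**Formula.** With equal arms,

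spurious difference = δ × [P(control | injured) − P(control | uninjured)],

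where P(control | injured) = p_C / (p_C + p_I) and P(control | uninjured) = (1 − p_C) / (2 − p_C − p_I).

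**Results for δ = 1 SD.**

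| p_C v p_I | P(control, given injured) | P(control, given uninjured) | Spurious difference |
|---|---|---|---|
| 20% v 20% | 0.20/0.40 = 0.50 | 0.80/1.60 = 0.50 | 0 |
| 30% v 20% | 0.30/0.50 = 0.60 | 0.70/1.50 = 0.467 | 0.13 SD |
| 30% v 10% | 0.30/0.40 = 0.75 | 0.70/1.60 = 0.4375 | 0.31 SD |
| 40% v 10% | 0.40/0.50 = 0.80 | 0.60/1.50 = 0.40 | 0.40 SD |
| 20% v 40% | 0.20/0.60 = 0.333 | 0.80/1.40 = 0.571 | −0.24 SD |

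The result scales with δ: at 30% v 10%, 0.5 SD gives 0.16 and 1.5 SD gives 0.47. Masking follows from the same formula. At 30% v 10%, a true within-arm difference of 0.31 SD is cancelled by a drug effect of −1 SD.

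**Effect of adjustment.** In simulation (6,000 trials per scenario, 30 per arm), a model with an arm term brought the spurious difference to about 0 in every scenario.

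**Centring the marker alone is not equivalent.** If expression is centred on its arm mean but the injury indicator is left as it is, a true within-arm difference shrinks by the factor [(p_C(1 − p_C) + p_I(1 − p_I))/2] / [p̄(1 − p̄)], where p̄ is the mean of the two rates.

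- 30% v 10%: [(0.21 + 0.09)/2] / (0.20 × 0.80) = 0.15/0.16 = 94%.
- 40% v 10%: [(0.24 + 0.09)/2] / (0.25 × 0.75) = 0.165/0.1875 = 88%.

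**Precision cost of an arm term.** For the same residual SD, the variance rises by the reciprocal of that factor: 1/0.9375 = 1.07 and 1/0.88 = 1.14. The standard error therefore rises by about 3% and 7%.

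**The case against.** The strongest reply is that row 4a is descriptive. It has no alpha and no rule for declaring a marker, and section 13.2.3 says: "Given the small sample sizes (n=30 in each of 2 treatment arms), modeling and testing will generally be restricted to the continuous endpoints". That is correct, and it limits the consequence. It does not remove the shift, which sits in the plotted and tabulated means whether or not a test is run.

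A reader might infer that any gene responding to the drugs will be reported as an injury marker. The documents do not support this. Bias needs unequal injury rates as well as a drug effect. Even if a 5% test were added, the simulation flagged a 1 SD drug-response gene in about 14% of trials at 30% v 10% and 23% at 40% v 10%, and at about the nominal rate when injury rates were equal.

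Other points on that side:

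- **Direction.** Section 12 suggests better renal function on belatacept but possibly more alloimmune injury. No single direction can be assumed for all the injury types in the row. This stands.
- **Contrast between arms.** Both arms receive tacrolimus to week 40, so only the week 52 scheduled sample follows planned withdrawal. The amendment also halted further withdrawal. The contrast is smaller than belatacept against tacrolimus alone. This stands, although the arms still differ in belatacept and in trough target.
- **Few events.** Renal biopsies are for cause only, so events may be sparse. Sparsity makes the bias harder to see, but does not remove it: at 15% v 5% the formula gives 0.75 − 0.85/1.80 = 0.28 SD.
- **Row 4b as safeguard.** It shows which markers differ by arm. It cannot tell a pure drug-response gene from an injury marker; a within-arm comparison can.
- **Other rows.** Rows 6, 7 (SNPs) and 9 are not stated by arm either, so row 4a is not alone in this.
- **Stated objective.** The phrase "how these associations may evolve over time and/or differ between therapeutic treatments" describes CTOT studies in general and concerns allograft rejection. It should not be read as a commitment that row 4a breaks.
- **Abbreviations.** CIT is Clinical Islet Transplantation in the glossary. Reading it as CNI toxicity is an inference from section 12.2.1. CHI is not in the glossary, and the method column has CKI in its place.

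**Conclusion.** The point holds in limited form. As written, row 4a does not separate association with injury from the effect of treatment. A drug-responsive gene can appear associated with injury, or a real marker can be masked, when injury frequency also differs between arms.

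Under the assumed 1 SD drug effect, the spurious difference runs from 0 at equal rates to 0.40 SD at 40% v 10%. The injury rates and drug effects are assumptions throughout. The flaw affects one exploratory row with no planned test, and does not touch the primary or secondary clinical analyses.

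**What to change.** In row 4a, replace the instruction to pool with: *both arms combined, adjusted for or stratified by treatment arm*. Either of these would serve:

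- an arm term or stratum in the comparison; or
- the event v no-event difference calculated within each arm and then combined across arms.

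Centring the marker alone should not be used, for the reason shown in the working. Show the plots coded by arm, and define CHI and CIT in the same edit.

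The cost is one line in Table 10 and no new data. Events from both arms still contribute, so this is not a split into two separate analyses. There is a small loss of precision, and where an arm has no events at a visit it adds nothing to the within-arm comparison at that visit.

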1.6 Mechanistic Secondary Endpoints

Samples for **Mechanistic studies** will be collected as specified on the SOE.

Immune Reactivity and Function

- 1. Multiparameter flow cytometric enumeration and phenotyping of peripheral blood leukocyte subsets. (Emory Cellular Core Laboratory)
- 2. Protective immunity (Emory Viral Surveillance Core Laboratory)
 - a. Viral load monitoring EBV, CMV, Polyoma BKV & JCV
 - b. Quantity and quality of CMV- and EBV- specific T cells and viral-specific antibody.
- 3. Anti-donor responses
 - a. Donor-specific antibody (Emory HLA Clinical Laboratory).
 - b. Immunohistochemistry of for-cause renal allograft biopsies (UCSF Pathology Core Lab).
 - d. Gene expression, mRNA profiling in blood, urine and tissue (University of Alabama Molecular Core Laboratory).
- 4. Serum and urine proteins, selected biomarkers of acute and chronic kidney injury (University of Alabama Protein Assay Core Laboratory).

Page 24 of 104

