13.2 Endpoint Assessments

13.2.1 Primary Clinical Endpoint

The primary endpoint will be the week-52 eGFR. Mean eGFR of the belatacept group will be compared to the mean eGFR of the tacrolimus reference group within a mixed models repeated measures (MMRM) framework , wherein repeated measures of eGFR at weeks 4, 12, 28, 36 and 52 will be modeled as a linear function of time (and perhaps other baseline covariates) in the 2 treatment groups. At week-52, a contrast will be made between the eGFR mean of the belatacept group and the eGFR mean of the tacrolimus group. ANCOVA assumptions will be evaluated graphically via standard residual analyses. If the assumptions fail, a suitable transformation (e.g., natural logarithms) will be found and the data will be reanalyzed on the transformed scale. Results will be reported with p-values associated with the F-test for each contrast and the corresponding mean treatment differences with two-sided 95% confidence intervals. All tests of significance will be two-tailed at the 0.05 level.

Estimating the contrasts within the repeated measures framework will provide treatment comparisons that are robust to subject dropout bias as long as the dropout pattern is missing at random²⁷. Data are missing at random whenever the "missingness" mechanism is a function of observable relationships among the nonmissing responses and covariates. Using the methods of Ma et al.²⁸, we will evaluate the MAR assumption in the data prior to implementing the MMRM analysis. If the MAR assumption fails, we will consider more robust alternatives (e.g., pattern mixture modeling)²⁹.

A number of studies have shown RMANCOVA to be superior to analyses of completers or of data with LOCF imputations³⁰. Nonetheless, we will conduct 2 related sensitivity analyses: (1) replace the missing week-52 values with the corresponding nonmissing week 36 values of each subject, dropping anyone who is missing both week-36 and week-52 and perform the ANCOVA as currently specified; (2) include only the completers in the ANCOVA analysis (i.e., exclude all dropouts). The sensitivity analyses will be included as additional secondary analyses.

13.2.2 Secondary Clinical Endpoints

The secondary endpoints are defined in Protocol section 1.5.

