The protocol defines 28 secondary clinical endpoints. The endpoints are to be computed and summarized by treatment and, in a few cases, by day/week and treatment. With the exception of specific AEs and lab parameters, proportions or means will be estimated for each treatment arm and tested for treatment differences through the use of a statistical model. The particular model to be used depends on the scale of measurement of the endpoint. The accompanying table lists each endpoint and its measurement scale (continuous, dichotomous, and ordinal). All tests of significance in all analyses will be made at the 0.05 level.

Dichotomous measures of prevalence and incidence will be analyzed with log-binomial regression models, wherein treatment effects will be estimated as relative risk ratios; the reference group will be the tacrolimus-thymoglobulin subjects. The log-binomial model (rather than logistic regression) is applied for prevalence and incidence analyses because model-based estimates of relative risk (RR) are both more desirable and appropriate for non-Poisson events that are expected to occur more commonly than in 10% of the cases. In such cases, logistic regression-based odds ratio (OR) estimates are poor estimators of the relative risk³¹,³²,³³,³⁴. It may be appropriate to treat some of the dichotomous outcomes as censored data; if this is the case, we will obtain RR estimates by fitting Cox regression models to the data³⁵.

The single ordinal secondary outcome variable (Banff cell-mediated AR score) will be analyzed in a proportional odds model³⁶ which may include additional covariates and interaction terms, as appropriate.

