13.3 Sample Size and Power Calculations

We have used data from the belatacept phase II and DIRECT studies and from the literature (Grewal and Blake 2005) to provide expected values for the GFR standard deviations shown in Table 10 below. Sample size calculations for these analyses were performed using NCSS-PASS software.

In the primary endpoint analysis, we will compare the mean GFR between the study groups at 12 months. With the sample sizes fixed, a priori, at 30 subjects in each of the two treatment arms, the following table shows the smallest treatment mean GFR differences (i.e. effect sizes) we will be able to declare significantly different, with 80% power and Type I error rates of 0.05 and 0.10:

Table 11 - Smallest Detectable Difference in GFR at 12 Months for Different Standard Deviationsand Alpha Levels

GFR Standard Deviation	Alpha Level	Smallest Detectable Difference in GFR (mL/min/1.7 m ²)
16	0.05	12.0
	0.10	10.5
20	0.05	15.0
	0.10	13.0
24	0.05	18.0
	0.10	16.0

This study has been powered to be able to detect minimum detectable differences in the primary endpoint at both the 0.05 and 0.10 levels that are clinically relevant as shown in Table 9 above. When reporting results of the primary endpoint analysis, we will report a p-value as significant at the 0.10 level if it is less than 0.10 and as significant at the 0.05 level if it is less than 0.05. As previously stated, all secondary endpoint analyses will be performed at the 0.05 level.

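### Analysis 4b tests more than 128 gene markers one at a time at a general 0.05 level with no false-discovery control; about 6 chance findings are expected if no marker truly differs

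*Combined protocol and SAP*

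**What the plan says.** Table 10 (section 13.2.3) has two gene-expression rows, both described as "Gene expression data for > 128 markers". Row 4a relates the markers to kidney injury and is labelled exploratory. Row 4b has a comparative aim, "Look for evidence of treatment differences in the occurrence of each marker over time", and its method is "Separate RMANCOVAs for each marker", with plots over time and tables of means and standard errors.

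Row 4b gives no significance level. Three general statements bear on it:

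- Section 13.2.2: "All tests of significance in all analyses will be made at the 0.05 level".
- Section 13.3: "all secondary endpoint analyses will be performed at the 0.05 level".
- The heading that lists gene expression among the endpoints: "1.6 Mechanistic Secondary Endpoints".

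The text of section 13.2.3 leaves room for either exploratory analysis or formal testing. It then says that testing will concentrate on treatment and time effects in continuous endpoints. Its worked example of an analysis with enough subjects to support inference is the repeated-measures ANCOVA of gene expression. A footnote to Table 10 makes tests conditional on adequate sample size. No multiplicity adjustment, false-discovery rule or ordering of the marker tests appears in the text.

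**The concern.** A per-test level of 0.05 controls error for one question. Row 4b asks the same question of more than 128 markers, so some will cross 0.05 when treatment has no effect on any of them. The plan has no rule for deciding which of the markers that cross should be taken seriously.

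What is at stake is the reading of the marker results. Section 13.8 commits the final report to the mechanistic analyses, so a list of nominally significant markers would be reported and could guide later work without any statement of how many are likely to be chance findings.

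**Working it through.** **Inputs**

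- Markers: more than 128 (Table 10); 128 is used as the floor. Table 7 (section 12.2.1) has 32 rows of 4 targets, which is 128. Three look like reference genes (b-actin, gapdh, 18S) and three look like repeats (MMP2 twice, PAI1/PAI-1, THBS1/Thrombospondin-1). That leaves 128 − 6 = 122.
- Level per test: 0.05, from the general statements in sections 13.2.2 and 13.3. It is taken as two-sided, as section 13.2.1 states for the primary analysis; the expected count does not depend on this.
- Subjects: 30 per arm. Assessment times: 5 (section 13.2.3).

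**The plan's own figure.** Section 13.2.3 gives error degrees of freedom of 58 for treatment and 238 for time and for time × treatment. These reproduce: 60 − 2 = 58, and 60 × (5 − 1) − 2 = 238 with time entered as linear. The model for one marker is not in question.

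**Expected false positives, one test per marker.** Expected count = number of markers with no true difference × 0.05.

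- 128 markers, none differing: 128 × 0.05 = 6.4.
- 122 markers, none differing: 122 × 0.05 = 6.1.
- 128 markers with a share truly differing (assumed shares): 10% gives 128 × 0.90 × 0.05 = 5.8; 20% gives 5.1; 30% gives 4.5; 50% gives 3.2.

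**Spread around 6.4.** With independent markers, P(at least one) = 1 − 0.95^128 = 99.9%, and the binomial P(at least three) is 95.7%. For correlated markers, 20,000 simulated trials were run with 128 equally correlated test statistics and no true differences (rho values assumed). The last column applies Benjamini-Hochberg at q = 0.05 to the same simulated trials.

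| rho | mean count | median | central 95% range | P(≥1) | P(≥3) | P(≥1) with Benjamini-Hochberg |
|---|---|---|---|---|---|---|
| 0 | 6.4 | 6 | 2 to 12 | 99.9% | 95.7% | 5.2% |
| 0.3 | 6.4 | 4 | 0 to 25 | 97.0% | 75% | 4.5% |
| 0.6 | 6.4 | 2 | 0 to 45 | 68.7% | 40% | 2.7% |

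Within simulation error the mean stays at 6.4, while the spread grows with rho. With Benjamini-Hochberg the mean number of false findings falls to 0.06, 0.16 and 0.68 for the three values of rho. At q = 0.10 the chance of any false finding under a complete null would be about 10% with independent markers, by construction of the method.

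**Cost of a stricter rule.** Bonferroni would use 0.05/128 = 0.00039. With 30 per arm and 80% power in a single-timepoint t-test, the detectable difference would rise from 0.74 SD to 1.20 SD. That is heavy for a screen, which is why false-discovery control is the better match.

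**The case against.** The strongest reply is that 4b is a screen in a small trial that section 2.2.2 itself calls exploratory. Its aim is worded as looking for evidence, section 13.2.3 permits exploratory analysis, and tests are run only where numbers are adequate. Plots and tables of means accompany the tests. If all p-values are reported, anyone can apply false-discovery control later without new data.

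Part of this stands. No trial decision rests on a marker, and the tables and plots give context. But row 4a carries the exploratory label and row 4b does not, and section 13.2.3 uses this very model as its example of an analysis fit for inference. The footnote concerns sample size, not the number of tests. Nothing commits the report to showing every p-value, and section 12.2.1 allows the gene targets to change, so the family could be unclear afterwards.

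It is also fair to say that the 0.05 level is inferred. The sentence in section 13.2.2 sits among the clinical endpoints, and section 13.3 refers back to it. Its wording covers all analyses, though, and section 1.6 makes these secondary endpoints, so 0.05 is the natural reading.

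A reader might infer larger totals. Reading both the treatment and the time × treatment test for each marker gives 256 × 0.05 = 12.8. Doing so in blood and in urine gives 512 × 0.05 = 25.6. The documents do not establish either. Degrees of freedom are given for both effects, and Appendix 2 schedules blood and urine for gene expression at the same five post-transplant visits. But the plan does not say which effects count as findings, and Table 7 is titled for kidney biopsies, so running the full panel in blood and urine is an assumption. Renal tissue is collected only for cause and does not fit a five-visit model.

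**Conclusion.** The point holds. Followed as written, analysis 4b yields about 6 false positives on average (6.4 for 128 markers, 6.1 for 122). This assumes that no marker truly differs, that one test is read per marker, and that the general 0.05 level applies to this row. The figure is a mean: with correlated markers a single trial could produce none or several dozen, and the mean falls to between 5.8 and 3.2 if 10% to 50% of markers truly differ. The totals of 12.8 and 25.6 are scenarios only.

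A reader might also conclude that real marker effects could not be separated from chance at all, or that the trial's main result is weakened. Neither follows. Effect sizes and time courses will be tabulated, adjustment is possible from the p-values if all are reported, and the primary eGFR contrast does not depend on the markers. This is an inexpensive improvement to how secondary mechanistic findings are interpreted.

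**What to change.** In row 4b of Table 10, specify:

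- Benjamini-Hochberg control across markers, applied separately within each specimen type and each effect tested, for example at 10%.
- A marker family fixed before unblinding, with reference genes and duplicates removed. Section 10.4.1 already keeps analyses blinded until database lock, so there is a natural date for this.
- A q-value reported beside the nominal p-value for every marker tested.
- A marker called different between arms only if it passes the false-discovery threshold. Markers that reach only nominal 0.05 are described as hypothesis-generating.

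The 10% level is an example; the team should choose and state one. The change needs a few words in the plan and a line of code, with no new subjects, visits or samples. The cost is that fewer markers will be called different. Reporting all nominal p-values limits that loss, because no result is hidden.
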